Statistical Analysis	
The primary study objective is to assess the overall response rate (ORR) of ramucirumab and pembrolizumab. The study will use Simon's two-stage design. Response rate with single agent IO is around 10% and we would consider a response rate of at least 25% to be interesting for further study. The initial stage will include 13 patients; the trial will be terminated if there are no responses. If the trial goes on to the second stage, an additional 21 patients will be included for a total of 34 patients studied.
 
Secondary objectives involve evaluating safety and tolerability and estimating PFS and overall survival. Descriptive statistics will be calculated for these outcomes and Kaplan-Meier curves will be calculated to estimate PFS and OS. Patients who have reached the end of the study but not progressed will be considered censored at the last documented date of contact. Estimates from this analysis will be used as preliminary data to inform future research.

IRB Protocol Number: 2019C0145
IRB Approval date: 06/10/2022
Version: 05/06/2022

PROTOCOL NUMBER: OSU-19132

LIST OF ABBREVIATIONS AND DEFINITIONS OF TERMS

ADR	Adverse Drug Reaction
AE	Adverse event
ALT (SGPT)	Alanine aminotransferase
ANC	Absolute neutrophil count
APC	Adenomatous polyposis coli
API	Active pharmaceutical ingredient
AST (SGOT)	Aspartate aminotransferase
AUC	Area under the curve
BMI	Body mass index
BSA	Body surface area
BUN	Blood urea nitrogen
BW	Body weight
CBC	Complete blood count
CI	Confidence interval
CK	Creatine kinase
CNS	Central nervous system
CR	Complete response
CRF	Case report form
CRO	Contract research organisation
CTCAE	Common terminology criteria for adverse events
CT Scan	Computed Tomography Scan
CYP450	Cytochrome P450
DCR	Disease control rate
DLT	Dose-limiting toxicity
DNA	Desoxyribonucleic acid
ECG	Electrocardiogram
ECOG	Eastern Cooperative Oncology Group
EOT	End of treatment
FU	Follow-up
GCP	Good Clinical Practice
GI	Gastrointestinal
GLP	Good laboratory practice
h	Hour
HR	Hazard ratio
IA	Interim analysis
IMP	Investigational medicinal product
INR	International normalized ratio
IRB	Institutional review board
ITT	Intent to treat
i.v.	Intravenous
KRAS	Kirsten Rat sarcoma
LDH	Lactate dehydrogenase
m ²	Square metre (body surface area)

IRB Protocol Number: 2019C0145
IRB Approval date: 06/10/2022
Version: 05/06/2022

PROTOCOL NUMBER: OSU-19132

mg	Milligram
min	Minute
mL	Millilitre
MRI	Magnetic resonance imaging
MTD	Maximum tolerated dose

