9.2 Sample Size Justification

Response rate with single agent IO is around 10% and we would consider a response rate of at least 25% to be interesting for further study. The optimal two-stage design to test the null hypothesis that $P \leq 0.10$ versus the alternative that $P \geq 0.25$ will include 13 patients in the first stage. After testing the drug on 13 patients in the first stage, the trial will be terminated if 1 or fewer respond. If the trial goes on to the second stage, an additional 21 patients will be included for a total of 34 patients studied.

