9.3 Planned Interim Analysis

After testing the drug on 13 patients in the first stage, the trial will be terminated if no patients respond. If the trial goes on to the second stage, an additional 21 patients will be included for a total of 34 patients studied.

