9.4 Analysis Plan

9.4.1 Primary endpoint analysis:

The primary study objective is to assess the overall response rate (ORR) of ramucirumab plus pembrolizumab. To do so, we will use Simon's two-stage design.²⁰ This design is implemented by first enrolling a small group of patients and then enrolling a second group of patients in the second stage conditional on an adequate number of responses in the first group. Response rate with single agent IO is around 10% and we would consider a response rate of at least 25% to be interesting for further study. The optimal two-stage design to test the null hypothesis that $P \leq 0.10$ versus the alternative that $P \geq 0.25$ will include 13 patients in the first stage. After testing the drug on 13 patients in the first stage, the trial will be terminated if 1 or fewer respond. If the trial goes on to the second stage, an additional 21 patients will be included for a total of 34 patients studied. If the

total number responding is less than or equal to 5, the drug is rejected. This design has an expected sample size of 20.95 and a probability of early termination of 0.621. The sample size was calculated using PASS 16 and assuming $\alpha = 0.10$ with a desired power of 80%.

Overall survival and progression-free survival as continuous time-to-event outcomes: All evaluable patients will be used for this analysis. Kaplan-Meier curves will be used to estimate overall survival, measured from the date of study registration to the date of event (i.e., death) or the date of last follow-up if no event has occurred at their last evaluation. We will further consider Cox proportional hazards models to explore a limited set of confounding factors.

9.4.2 Analysis of secondary endpoints:

Secondary objectives involve evaluating safety and tolerability and estimating PFS and overall survival. Descriptive statistics will be calculated for these outcomes and Kaplan-Meier curves will be calculated to estimate PFS and OS. Patients who have reached the end of the study but not progressed will be considered censored at the last documented date of contact. Estimates from this analysis will be used as preliminary data to inform future research.

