Overall response. All evaluable patients (i.e. eligible patients who have received at least one dose of the treatment) will be assessed in terms of their best response to therapy. Those who achieve a partial response (PR) or complete response (CR) will be considered responses and the overall response rate will be calculated as the number of PRs and CRs divided by the total number of evaluable patients. We will also perform analysis of disease control rate (CR + PR + SD). These estimates will be accompanied by exact binomial confidence intervals as well.

Safety and Tolerability. Frequency and severity of adverse events and tolerability of the regimen will be collected and summarized by descriptive statistics for each of the disease cohorts. As per NCI CTCAE v 5.0, the term toxicity is defined as adverse events that are classified as either possibly, probably, or definitely related to study treatments. The maximum grade for each type of toxicity will be recorded for each patient, and frequency tables will be reviewed to determine toxicity patterns. In addition, we will review all adverse event data that is graded as 3, 4, or 5 and classified as either “unrelated” or “unlikely to be related” to study treatment in the event of an actual relationship developing. The incidence of severe (grade 3+) adverse events or toxicities will be described. We will also assess tolerability of the regimens through assessing the number of patients who required dose modifications and/or dose delays. In addition, we will also capture the proportion of patients who go off treatment due to adverse reactions or even those who refuse further treatment for lesser toxicities that inhibit their willingness to continue participation on the trial. All patients who have received at least one dose of the therapeutic agent in this study will be evaluable for toxicity and tolerability. This is detailed in Table 7.

Table 7: Evaluating Adverse Events

V5.0 CTCAE Grading	Grade 1	Mild; asymptomatic or mild symptoms; clinical or diagnostic observations only; intervention not indicated.
	Grade 2	Moderate; minimal, local or noninvasive intervention indicated; limiting age-appropriate instrumental ADL.
	Grade 3	Severe or medically significant but not immediately life-threatening; hospitalization or prolongation or hospitalization indicated; disabling; limiting self-care ADL.
	Grade 4	Life threatening consequences; urgent intervention indicated.
	Grade 5	Death related to AE

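### The ORR interval in Section 9.4.2 has no stated confidence level and ignores the stage 1 stop; under the stop at 1 or fewer of 13 its upper limit is too low (minor reporting point).

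*Combined protocol and SAP*

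**What the plan says.** Section 9.4.1 tests a response rate of at most 10% against at least 25% with Simon's optimal two-stage design: 13 patients, then 21 more, 34 in total. Alpha is 0.10 (sidedness not stated) and desired power is 80%. The final decision is a count: if the "total number responding is less than or equal to 5, the drug is rejected". Section 9.4.1 adds: "This design has an expected sample size of 20.95 and a probability of early termination of 0.621".

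Estimation of ORR is described only in Section 9.4.2, under secondary endpoints. Evaluable patients are "eligible patients who have received at least one dose of the treatment", and "the overall response rate will be calculated as the number of PRs and CRs divided by the total number of evaluable patients". After mentioning disease control rate as well, the section says: "These estimates will be accompanied by exact binomial confidence intervals as well". No level is given for either rate, and no interval that allows for the interim stop is named. The only numeric level for a planned analysis is the 95% in Section 9.5, which applies to continuous correlative markers.

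The stage 1 rule itself is stated in two ways. Section 9.2 (and 9.4.1) says "the trial will be terminated if 1 or fewer respond". Section 9.3 says "the trial will be terminated if no patients respond", and the Synopsis (Statistical Analysis) says "the trial will be terminated if there are no responses".

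**The concern.** A fixed-sample exact interval treats the 34 patients as a single sample. In this trial a result out of 34 exists only if stage 1 passed its boundary, so trials that stop early are part of the distribution and rank below every completed trial. The interval therefore loses its exact guarantee, mainly at the upper end, and it need not agree with the two-stage test.

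The level is also open. In an open-label single-arm trial the count is known when the report is written. If the level is not fixed beforehand, the same result can be described as excluding or not excluding the 10% benchmark.

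**Working it through.** **Inputs.** From Section 9.4.1: p0 = 0.10, p1 = 0.25, n1 = 13, n = 34, success at 6 or more responders. From Sections 9.2 and 9.4.1: stop at 1 or fewer of 13. From Section 9.3 and the Synopsis: stop at 0 of 13. Assumptions: exact binomial means Clopper-Pearson; alpha 0.10 is one-sided, so the matching two-sided level is 80%; 34 patients are evaluable unless stated otherwise.

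**Step 1: reproduce the plan's figures.** Under p0, with the stop at 1 or fewer:
- P(stop) = 0.9^13 + 13 × 0.1 × 0.9^12 = 0.2542 + 0.3672 = 0.621
- E[N] = 13 + 21 × (1 − 0.6213) = 20.95

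Both agree with Section 9.4.1. The stop at zero gives 0.254 and 13 + 21 × 0.7458 = 28.66, which do not.

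**Step 2: tail probabilities.** Let T(x, p) = sum over k ≥ 2 of P(X1 = k | 13, p) × P(X2 ≥ x − k | 21, p).
- Two-stage: T(6, 0.10) = 0.0957, so alpha is met. T(6, 0.25) = 0.811, so power is met.
- Single-stage: P(X ≥ 6 | 34, 0.10) = 0.1185.
- The difference, 0.0228, belongs to trials with 0 or 1 responder in stage 1 (0.0037 + 0.0191), which would have stopped.

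**Step 3: intervals.** With a = (1 − level)/2, Clopper-Pearson solves P(X ≥ x | 34, p) = a and P(X ≤ x | 34, p) = a. The two-stage interval solves T(x, p) = a and 1 − T(x + 1, p) = a. All figures below use the stop at 1 or fewer.

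| Result | Method | 80% | 90% | 95% |
|---|---|---|---|---|
| 6/34 | Clopper-Pearson | 9.5–28.9% | 8.0–31.9% | 6.8–34.5% |
| 6/34 | Two-stage | 10.1–30.9% | 8.4–34.5% | 7.1–37.9% |
| 7/34 | Clopper-Pearson | 11.8–32.2% | 10.1–35.2% | 8.7–37.9% |
| 7/34 | Two-stage | 12.2–33.3% | 10.4–36.7% | 9.0–39.8% |
| 8/34 | Clopper-Pearson | 14.2–35.4% | 12.3–38.5% | 10.7–41.2% |
| 8/34 | Two-stage | 14.5–36.0% | 12.5–39.2% | 10.9–42.2% |

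- *Upper limit.* At the Clopper-Pearson 95% upper limit for 6/34 (34.5%), the fixed-sample probability of 6 or fewer is 2.5%. The two-stage probability of stopping or finishing with 6 or fewer is 4.9%.
- *Level.* At 7/34 the level decides whether 10% is excluded, under either method. With Clopper-Pearson this is the only such count: at 6/34 all three intervals include 10%, and at 8/34 all three exclude it.
- *Agreement with the test.* At 6/34 the 80% Clopper-Pearson interval includes 10%, although the count rule rejects it. The two-stage 80% interval excludes 10%. At 90% and 95% both methods include 10%, so at those levels the difference from the test is one of level.

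Under the stop at 1 or fewer, P(6/34) is 12.3%, 12.7% and 8.0% at true rates of 15%, 20% and 25%. P(7/34) is 9.7%, 14.1% and 11.8%.

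**Step 4: how far this holds.**
- *Evaluable number.* With 6 responders, the 80% Clopper-Pearson lower limit is 9.5% at 34 evaluable, 9.8% at 33, 10.2% at 32 and 10.5% at 31. The conflict exists only at 33 or 34.
- *Stop at zero.* Alpha is 0.115. The two-stage 80% interval at 6/34 is 9.6–29.1%, which still includes 10%. The 95% upper limit is 34.9%, close to the 34.5% from Clopper-Pearson. The level issue at 7/34 remains.
- *Two-sided coverage of Clopper-Pearson (stop at 1 or fewer).* At p = 0.10 it is 95.8%, 95.8% and 98.4% for nominal 80%, 90% and 95%. At p = 0.25 it is 89.5%, 92.8% and 96.0%. The minima are 76.1% (nominal 80%) and 87.1% (nominal 90%). Coverage is below nominal at only 3.6% and 4.6% of true rates between 0.10 and 0.35, and nowhere in that range at 95%.
- *Upper-limit misses.* For true rates from 0.10 to 0.40 these reach about 14%, 8% and 4%, against nominal 10%, 5% and 2.5%.

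**The case against.** The strongest reply is that the interval is descriptive. Section 9.4.1 decides on the count and never uses the interval as a test, and Section 9.4.2 presents its estimates as preliminary data for later research. A descriptive interval need not invert the test, and two-sided coverage is above nominal at both design rates. All of this stands.

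A reader might infer that the plan's interval contradicts the plan's test. The documents do not support that: nowhere do they plan an 80% interval. That level comes only from reading alpha 0.10 as one-sided. Even then the conflict needs 33 or 34 evaluable patients, and the two-stage interval removes it only under the stop at 1 or fewer.

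Another fair objection is that a two-stage interval quoted at both 80% and 95% would give different messages about 10% at 6/34 (10.1% against 7.1%) and at 7/34 (12.2% against 9.0%), whereas the Clopper-Pearson levels differ only at 7/34. That is a reason to name one primary level.

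The objection does not dispose of two facts. The level is missing, and the fixed-sample upper limit is too low for the design in Sections 9.2 and 9.4.1, where an exact alternative costs little.

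**Conclusion.** The point holds as a minor reporting improvement. Under the stop at 1 or fewer of 13, the planned interval has an upper limit that is too low, by 3.4 percentage points at 6/34 and 95% (37.9 − 34.5). At 7/34 the unstated level decides whether 10% is excluded.

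Two further inferences should be avoided. The go/no-go decision is not at risk, because it rests on the count. The planned interval is not seriously anti-conservative either: the excess misses lie at the upper limit, and two-sided coverage is near or above nominal over almost all of the relevant range.

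The figures assume Clopper-Pearson, 13 and 34 evaluable patients, and stopped trials ranked below completed ones. The 80% comparison also assumes a one-sided alpha. The size of the upper-limit shortfall, and any gain in agreement with the test at 6/34, depend on which stage 1 rule applies.

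**What to change.** First reconcile the stage 1 rule between the Synopsis and Section 9.3 on one side and Sections 9.2 and 9.4.1 on the other. Then state in Section 9.4.2:

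- The primary ORR interval is computed from the two-stage sample space of the reconciled rule, using the evaluable numbers attained at each stage.
- It has one pre-stated level: two-sided 80% if it is meant to match the test. Any other level, and any Clopper-Pearson interval, is labelled descriptive.
- The disease control rate interval also has a stated level.

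If the two-stage interval is not adopted, state the level of the planned interval and say that it ignores the interim stop.

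The cost is two or three sentences and a short calculation, with no new data. The interval becomes slightly wider (at 6/34 and 80%, 20.8 points instead of 19.4) and must be recomputed if the evaluable numbers differ from 13 and 34.

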Relationship to Investigational Product	Did investigational agent cause the adverse event? The determination of the likelihood that investigational agent caused the adverse event will be provided by an investigator who is a qualified physician. The investigator's signed/dated initials on the source document or worksheet that supports the causality noted on the AE form, ensures that a medically qualified assessment of causality was done. This initialed document must be retained for the required regulatory time frame. The criteria below are intended as reference guidelines to assist the investigator in assessing the likelihood of a relationship between the test drug and the adverse event based upon the available information. The following components are to be used to assess the relationship between investigational agent and the AE; the greater the correlation with the components and their respective elements (in number and/or intensity), the more likely investigational agent caused the adverse event (AE):
Exposure	Is there evidence that the participant was actually exposed to investigational agent such as: reliable history, acceptable compliance assessment (pill count, diary, etc.), expected pharmacologic effect, or measurement of drug/metabolite in bodily specimen?
Time Course	Did the AE follow in a reasonable temporal sequence from administration of investigational agent? Is the time of onset of the AE compatible with a drug-induced effect (applies to trials with investigational medicinal product)?
Likely Cause	Is the AE not reasonably explained by another etiology such as underlying disease, other drug(s)/vaccine(s), or other host or environmental factors

9.5 Analysis of Exploratory Endpoints - Correlative studies:

Several correlative markers will be explored in this trial in relation to clinical outcomes of interest, and in particular in relation to the primary endpoint of response rate. Statistical analysis corresponding to the correlative studies will be descriptive and exploratory in nature.

For immune cell subpopulation data by flow cytometry, we will identify differences between the paired PBMC samples from the same patients. TCR immunoSEQ data will be summarized for each patient for T-cell clonality difference, descriptive statistics and confidence interval will be obtained across patients.

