To study the association of immune cell subpopulations among blood and the tumor microenvironment, we will use linear mixed-effects models for repeated measurements within patients. A bivariate plot will be used to describe the relationship between response rate and peak VEGF via ELISA over time. Results will be summarized using descriptive statistics (i.e. means, medians, standard deviations, 95% confidence intervals for continuous variables, and frequencies for discrete data). The limited sample will not provide sufficient power for formal hypothesis testing (except to detect very large differences in these markers), but the preliminary data will be used to explore potential relationships and differences using graphical analyses and quantitative summaries of these markers. These results and exploratory analyses will also be used in planning a future randomized study of this combination treatment regimen in this patient population.

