APPENDIX 1 RECIST 1.1 CRITERIA

RECIST 1.1 will be used as the primary measure for assessment of tumor response, date of disease progression, and as a basis for all protocol guidelines related to disease status (eg, discontinuation of study treatment). Although RECIST 1.1 references a maximum of 5 target lesions in total and 2 per organ, the Sponsor allows a maximum of 10 target lesions in total and 5 per organ, if clinically relevant to enable a broader sampling of tumor burden. All patients will have their BEST RESPONSE on study classified as outlined below:

Complete Response (CR)

Disappearance of all target lesions. Any pathological lymph nodes (whether target or non target) must have reduction in the short axis to <10mm.

Partial Response (PR)

At least a 30% decrease in the sum of diameters of target lesions, taking as reference the baseline sum LD.

Stable Disease (SD)

Steady state of disease. Neither sufficient shrinkage to qualify for PR nor sufficient increase to qualify for PD.

Progressive Disease (PD)

At least a 20% increase in the sum of diameters of measured lesions taking as references the smallest sum of diameters recorded since the treatment started. In addition to the relative increase of 20%, the sum must also demonstrate an absolute increase of at least 5 mm. Appearance of one or more new lesions will also constitute progressive disease.

Response Duration

Response duration will be measured from the time measurement criteria for CR/PR (whichever is first recorded) are first met until the first date that recurrent or progressive disease is objectively documented, taking as reference the smallest measurements recorded since the treatment started.

Stable Disease Duration

Stable disease duration will be measured from the time of start of therapy until the criteria for progression are met, taking as reference the smallest measurements recorded since the treatment started.

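### The correlative plan singles out yes/no response as the marker outcome; adding percentage tumor change, which is already measured, is a cheap improvement

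*Combined protocol and SAP*

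**What the plan says.** Section 2.3 sets out to characterize immunologic markers that predict response. Section 9.5 then explores the markers against "clinical outcomes of interest, and in particular in relation to the primary endpoint of response rate". The one display it names that pairs a marker with an outcome is for VEGF: "A bivariate plot will be used to describe the relationship between response rate and peak VEGF via ELISA over time". The other named analyses do not involve response. They are within-patient PBMC differences, a summary of T-cell clonality, and a mixed model of immune cells in blood and tumor. The section calls the work descriptive and exploratory, and concedes: "The limited sample will not provide sufficient power for formal hypothesis testing".

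Section 9.4.2 counts a patient with CR or PR as a responder. Appendix 1 defines PR by a threshold: "At least a 30% decrease in the sum of diameters of target lesions". Section 6.1.1 has response judged against the baseline tumor measurement at each scheduled CT, and Section 4.2 requires measurable disease at entry. The uncut percentage change is therefore available for every patient who has an on-study scan. No section plans to analyze it.

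**The concern.** Response rate is a group figure. For a single patient it is 0 or 1, so a plot of a continuous marker against it is two columns of points, one of them nearly empty. A 29% shrinkage counts the same as rapid growth, and a 31% shrinkage the same as a complete response.

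Section 9.5 blames its low power on the limited sample and says the results will help plan a randomized study. Part of that limit may come from the outcome scale. If so, a marker with a moderate, graded relation to tumor shrinkage could be overlooked or estimated very loosely, when the same patients' scans could show it. After a poor stage 1 with no responders, a marker-by-response comparison would not exist at all.

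**Working it through.** **Inputs.** The rates come from Section 9.4.1, which tests the "null hypothesis that $P \leq 0.10$ versus the alternative that $P \geq 0.25$ will include 13 patients in the first stage". The maximum size comes from the same section: "an additional 21 patients will be included for a total of 34 patients studied". The text of Section 6.1.3 describes CyTOF collection for the 13 stage 1 patients, although the specimen table there states no such limit.

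**The plan's own figures.** Under the 9.4.1 rule ("the trial will be terminated if 1 or fewer respond"), early termination at 10% has probability 0.9^13 + 13 × 0.1 × 0.9^12 = 0.254 + 0.367 = 0.621. The expected size is 13 + 21 × (1 − 0.621) = 20.95. Both match the stated values. Section 9.3 gives a different rule ("the trial will be terminated if no patients respond"), under which early termination has probability 0.254 and the expected size is 28.7. That conflict is a separate matter. Here it only changes how likely it is that 34 patients are reached.

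**Expected responders (N × p).**
- 34 patients: 34 × 0.10 = 3.4 and 34 × 0.25 = 8.5.
- 13 patients: 13 × 0.10 = 1.3 and 13 × 0.25 = 3.25.

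**Information kept by the cut.** Assume that marker and tumor change are jointly normal, and that response is the lowest fraction p of tumor change. For weak associations, the efficiency of the binary outcome relative to the uncut one is φ(z_p)² / [p(1 − p)].
- p = 0.10: 0.1755² / 0.09 = 0.342, so 34 patients act like 11.6 (a 66% loss).
- p = 0.25: 0.3178² / 0.1875 = 0.539, so 34 patients act like 18.3 (a 46% loss).

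**Precision of the responder comparison.** Since the plan is descriptive, interval width is a fair yardstick. The 95% half-width for a difference in marker means is about 1.96 × √(1/k + 1/(34 − k)) marker SDs, where k is the number of responders.
- k = 3: 1.96 × 0.605 = 1.19 SD.
- k = 9: 1.96 × 0.389 = 0.76 SD.

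**Simulated power, n = 34, two-sided 5%.** The 5% level is my assumption, as the plan sets none here. Each cell gives the results at response rates of 10% and 25%.

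| Assumed pattern | Mann-Whitney by response | Spearman with tumor change |
|---|---|---|
| Graded, correlation 0.4 | 0.24, 0.39 | 0.61, 0.62 |
| Graded, correlation 0.5 | 0.34, 0.56 | 0.82, 0.83 |
| Only responders differ, by 1.5 SD | 0.58, 0.92 | 0.20, 0.65 |

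The last row reverses the ranking.

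**Stage 1 only, n = 13.** With one responder, the smallest possible two-sided exact Mann-Whitney p-value is 2/13 = 0.15. With three responders and a graded correlation of 0.7, power is about 0.40 by response and about 0.75 by Spearman. At correlation 0.5, Spearman itself reaches only about 0.39.

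**The case against.** The strongest reply has four parts.

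- **Scope.** A reader might infer that Section 9.5 ties every marker to yes/no response. It does not. It speaks of clinical outcomes generally and only singles response out. Survival and disease control are also listed outcomes of the trial, and three of the named analyses do not use response. This stands. The supportable claim is that response is the only outcome Section 9.5 singles out, and the only one in a named marker-outcome display.

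- **Size of the loss.** A reader might also infer that half to two thirds of the information is lost as a matter of fact. The documents do not say whether any marker is graded with tumor change or marks out responders alone. In the second case the binary split does better. This stands too, and it argues for showing both scales.

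- **A different quantity.** Best change in target lesions is not simply response without the cut. New lesions count as progression in Appendix 1, and Section 6.3.5 asks for responses to be confirmed by a repeat scan at least 4 weeks later. Target-lesion change ignores both. This is a reason not to demote response. It is no reason to leave the measurement unused.

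- **Exploratory status.** The plan disclaims formal testing and allows for graphical summaries, which do not exclude a plot against tumor change. That lowers the severity. It does not remove the point, because a plot or an interval with 3 to 9 patients in one group is also uninformative, and no section commits to the alternative.

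**Conclusion.** The point holds as a low-severity, cheap improvement. Section 9.5 steers the marker work toward a yes/no outcome with about 3 to 9 responders in at most 34 patients, or about 1 to 3 in the 13 for whom CyTOF is described. The percentage change that is already measured goes unused.

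Under a graded, roughly linear relation with joint normality, the cut keeps about 34% to 54% of the information. If only responders differ in the marker, the advantage of the uncut scale shrinks or reverses. The figures for 34 patients apply only if the trial reaches stage 2. With 13 patients, power stays low on either scale except for strong associations, but the uncut measure can still be analyzed when stage 1 yields no responder or one.

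The documents do not support replacing response as the marker outcome. Nothing here touches the primary ORR test, the secondary endpoints or the sample size.

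**What to change.** In Section 9.5, add best percentage change from baseline in the RECIST 1.1 target-lesion sum of diameters as a continuous outcome, co-reported with CR/PR.

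- For each marker, give a scatter plot and a Spearman correlation with a 95% confidence interval.
- On the VEGF plot, use this measure as the outcome axis and mark the responders.
- Give patients with no post-baseline scan because of death or clinical progression the worst tied rank.
- Flag patients with new-lesion or non-target progression on the plots.
- Keep the responder comparison, the primary ORR and the Simon design as they are.

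The cost is a few sentences and a small amount of analysis on data already held, with no added patients, scans or samples. The downside is that target-lesion change ignores new and non-target lesions and the confirmation of response. The flags and the retained responder comparison keep that visible.
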